2. Study Objectives: The objective of this study is to investigate the neural mechanisms of gait adaptation and the effects of transcutaneous electrical nerve stimulation (TENS) on adaptability during split-belt treadmill training in PwMS. Functional near-infrared spectroscopy (fNIRS) will be used during a split-belt treadmill training paradigm to assess cortical activation during gait adaptation. Additionally, the effect of split-belt treadmill training coupled with TENS on gait adaptability in PwMS will be tested with active and inactive TENS during split-belt treadmill sessions. Cortical activation and the effect of TENS on gait adaptability will be compared between neurotypical adults and PwMS to assess differences that can be attributed to multiple sclerosis. Specifically, we hypothesize that the sensorimotor integration areas of the cortex including the supplementary motor areas (SMA), premotor cortex (PMC), somatosensory cortex (S1), and posterior parietal cortex (PPC) will have heightened activity during split-belt treadmill training, compared to when the belts are moving the same speed. Additionally, we hypothesize that the application of TENS during split-belt treadmill training will significantly increase gait symmetry improvements when compared to split-belt treadmill training alone and will also result in improved adaptation retention.

B. Background and Significance

1. Study Significance: Studies have consistently demonstrated that split-belt treadmill training can acutely improve gait symmetry, however there is minimal application of this paradigm toward enhancing or prolonging these improvements. The impact of this study is not only revealing the cortical mechanisms of sensorimotor adaptation and improving gait symmetry, but a necessary step towards translating these improvements out of the lab into a real-world environment thereby persistently improving mobility for not only PwMS but the tens of millions of individuals who experience gait dysfunction.

INSTITUTIONAL REVIEW BOARD NON-EXEMPT PROTOCOL TEMPLATE

2. Our recent studies showed robust gait symmetry improvements in PwMS following split-belt treadmill training and additionally has demonstrated that TENS improves positional awareness and motor learning during a stepping task. The combination of these findings leads us to want to investigate the neural mechanisms of split-belt treadmill training and if TENS can enhance to effects of split-belt treadmill training.

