A. Study Type and Design: This is a crossover study with both PwMS and age and sex-matched neurotypical controls. 30 PwMS and 20 neurotypical controls be randomized into two groups and will participate in two split-belt treadmill training sessions while outfitted with cortical fNIRS and TENS devices on their bilateral tibialis anterior and rectus femoris. The first group will complete split-belt treadmill training with TENS OFF during the first visit and TENS ON during the second visit. The second group will complete split-belt treadmill training with TENS ON during the first visit and TENS OFF during the second visit to control for a learning effect. In between visits there will be a 4-week washout period. Participants will receive TENS only during the 10-minute split-belt adaptation period of the paradigm. During all other periods the TENS will be OFF.

B. Sample size, statistical methods, and power calculation

1. Total number of subjects who will be approached (including screen fails, controls and subject withdrawals) to reach enrollment numbers for the lifetime of the study for this investigator's site: 60
2. Total number of subjects to be enrolled at this site: 50

INSTITUTIONAL REVIEW BOARD NON-EXEMPT PROTOCOL TEMPLATE

3. Brief Description/justification for the proposed sample size in *lay terms*: From our preliminary data we computed a large effect size of 1.01 for change in brain activity in the SMA from baseline walking to split-belt treadmill training. According to our power analysis, to maintain an alpha of 0.05 and a power of 0.8, at least 10 participants per group are needed to detect significant changes in brain activity.
4. Simple randomization will occur (TENS first or TENS second) for both groups (PwMS and neurotypical controls).
5. No masking will occur in this study.

C. Subject Criteria (See Vulnerable Populations appendix 1, if applicable): PwMS and neurotypical controls from ages 18-86. All races and genders are included.

1. Inclusion criteria:

- A diagnosis of relapsing remitting multiple sclerosis OR a neurotypical adult (ages 18-86)
- Not experiencing an active relapse
- Able to stand and walk without an assistive device
- Able to walk for three tenths of a mile without stopping to rest
- MS participants must have a neurologist confirmed diagnosis of relapsing-remitting MS.
- MS participants must be independently ambulatory in the community, expanded disability status scale (EDSS) score < 5 (clinical measure of MS severity).

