- **Cortical Activation via fNIRS.** All fNIRS data will be acquired using a mobile NIRS Sport2 device (NIRx Medical Technologies, nirx.net), which will be secured to participants' backs using backpack-like straps and buckles. This head probe was designed to measure regions of interest (ROI) that were established a priori. The Juelich atlas within the fNIRS Optodes Location Decider (fOLD) toolbox in MATLAB was used to design our optode montage which identifies channel locations above superficial components of the frontal, motor, and sensory regions. Our fNIRS head probe will include 16 sources and 15 detectors which will create 48 channels over the designated ROIs (Figure 1). Additionally, eight short-separator detectors will be used to measure scalp perfusion. All fNIRS data will be acquired and streamed to a laptop using Aurora software v.2021.9 (NIRx Medical Technologies, nirx.net/aurora). Raw fNIRS data will be processed using a commercial software tool, Satori v.1.8 by Brain Innovation (NIRx Medical Technologies, nirx.net/satori) to perform pre-processing steps, such as motion artifact removal, physiological noise detection, and channel selection and removal. Following, the raw light intensity data will be converted to optical density values and then converted to oxygenated hemoglobin (HbO), deoxygenated hemoglobin and total hemoglobin values using the Modified Beer-Lambert Law automatically through Satori software. The HbO beta values calculated from general linear models will be used as a proxy for cortical activity, and we will measure changes in HbO beta between each protocol period described in Figure 2B.

[figure not shown]

Figure 1. Optode montage (16x15) created using Brodmann atlas within fOLD to allow measurement of cortical hemodynamics for premotor, sensorimotor, and posterior parietal regions. Each red circle indicates a source optode, each blue circle represents a detector optode, and each purple connecting line represents a unique channel.

2. Study Procedures:

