- **Split-belt Treadmill Training Paradigm.** The participants will be outfitted with 6 APDM Opal inertial sensors (APDM Inc, Portland, OR) as well as 16 retroreflective markers for collection of three-dimensional motion capture data during a 10-minute split-belt treadmill training paradigm (Figure 2). For the overground walking portion, participants will be asked to walk back and forth down a 30m hallway for 2 minutes while APDM Mobility Lab is collecting inertial sensor gait cycle parameters. For the treadmill portion, participants will be asked to walk on a custom-built instrumented,

INSTITUTIONAL REVIEW BOARD NON-EXEMPT PROTOCOL TEMPLATE

split-belt treadmill with two Bertec force platforms (Model 4060-10, Bertec Corp, Columbus, OH) consisting of two separate belts, each with its own motor that permits the speed of each belt to be controlled independently and collects ground reaction forces at 1000 HZ. The speed at which a participant is walking will be individualized to their overground preferred walk speed and fast walk speed. Specifically, during the tied-belt walking period, the belts will be set to the overground preferred walking speed. During split-belt treadmill adaptation period, the “fast belt” speed will be equal to the participant’s fast walk speed while the “slow belt” speed will be one half of the participants fast walk speed (2:1 ratio). Prior

[figure not shown]

Figure 2. (Top) Time course for the split-belt treadmill training paradigm depicting the stages of baseline, adaptation, and deadadaptation (**Top**) fNIRS block design collection protocol. Following a 1-minute baseline rest period, fNIRS will be collected during tied-belt walking, split-belt treadmill training, and deadadaptation utilizing an average of two 30-second blocks for each period of the paradigm to assess differences in activation between each period.

research has determined that the “fast belt” speed should be set for the more affected leg to improve gait asymmetry. Following the adaptation period, a 10-minute deadadaptation period with the belts tied at the preferred speed will occur to monitor gait symmetry changes during deadadaptation between groups.

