- C. Statistical Analysis Plan:** In this crossover design, PwMS and healthy control participants will be pseudo-randomized to begin in either the TENS First or TENS Second condition. Randomization will be performed using a random number generator and will be counterbalanced across age, sex, and fast limb to ensure group balance. A predefined list of participant numbers with corresponding randomized assignments will be generated prior to enrollment. Linear mixed-effects models will be used to identify differences in adaptation and fNIRS outcomes, with group (PwMS vs. healthy controls), visit (Visit 1 vs. Visit 2), and TENS condition (TENS ON vs. TENS OFF), along with their interactions, as fixed effects, and participant number as a random effect. Assumptions of linearity, normality of residuals, and homoscedasticity will be tested for each model. Following model creation, a repeated measures ANOVA will be performed for each adaptation outcome (adaptation rate and adaptation savings) and for cortical activation (HbO beta). Type III ANOVAs with Satterthwaite's method for degrees of freedom estimation will be used for all analyses. Post-hoc comparisons will be conducted using estimated marginal means (EMM) to further investigate significant main effects and interactions. P-values will be corrected using the Benjamini–Hochberg false discovery rate within each outcome and group when applicable. Cohen's d will be calculated to quantify effect sizes. Separate regression models will be conducted to assess the influence of demographic covariates on primary outcome models. All statistical analyses will be conducted using the lme4 and emmeans packages within R and were two-tailed with an alpha threshold set at 0.05.

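### The planned fNIRS model contains no test of split-belt versus tied-belt activity, the cortical hypothesis on which the sample size rests

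*Combined protocol and SAP*

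**What the plan says.** - **Hypothesis (I.A.2, Study Objectives).** SMA, PMC, S1 and PPC are named, with the prediction that they "will have heightened activity during split-belt treadmill training, compared to when the belts are moving the same speed".
- **Sample size (II.B.3).** The only calculation takes from preliminary data an "effect size of 1.01 for change in brain activity in the SMA from baseline walking to split-belt treadmill training". With alpha 0.05 and power 0.8 it concludes that "at least 10 participants per group are needed to detect significant changes in brain activity".
- **Measurement (III.D.1, Cortical Activation via fNIRS; III.D.2, Figure 2 caption).** HbO beta is the proxy for cortical activity, and "we will measure changes in HbO beta between each protocol period described in Figure 2B". Recordings cover tied-belt walking, split-belt training and deadaptation, "utilizing an average of two 30-second blocks for each period of the paradigm to assess differences in activation between each period".
- **Analysis (V.C, Statistical Analysis Plan).** One mixed-model structure serves both the adaptation and the fNIRS outcomes. Its fixed effects are "group (PwMS vs. healthy controls), visit (Visit 1 vs. Visit 2), and TENS condition (TENS ON vs. TENS OFF), along with their interactions", with participant as a random effect, followed by Type III ANOVA. Then: "Post-hoc comparisons will be conducted using estimated marginal means (EMM) to further investigate significant main effects and interactions". P-values are adjusted by the Benjamini–Hochberg "false discovery rate within each outcome and group when applicable". The only other models concern demographic covariates.
- **Participants (II.A; III.D.2, TENS Protocol).** II.A gives 30 people with MS and 20 controls; the TENS Protocol gives 30 and 30. The TENS Protocol also identifies those with TENS OFF at visit 1 as the Aim 1 participants.

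**The concern.** The hypothesis and the sample size both concern a difference between two walking periods within the same person. The analysis plan has no factor for period and does not define the fNIRS outcome as a particular difference between periods. Its terms ask whether activation differs by group, by visit or by TENS, which are different questions.

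If V.C were followed exactly, the contrast for which the trial was sized would have no planned test. Any test added later would leave open which periods are compared, which participants are used and how the four regions are corrected. II.B.5 states that there is no masking, and III.N.1 plans rolling review of the data, so those choices could be made with results in view.

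**Working it through.** **1. Reproduce the plan's figure.** Inputs: d = 1.01, alpha 0.05 and power 0.8 (II.B.3); two-tailed testing (V.C). For a paired t-test on the within-person change, power = P(|T| > t(0.975, n−1)), where T is noncentral t with n−1 degrees of freedom and noncentrality d√n.

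- n = 9: noncentrality 1.01 × √9 = 3.03, critical value 2.306, power 0.756.
- n = 10: noncentrality 1.01 × √10 = 3.19, critical value 2.262, power 0.811.

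So 10 is the smallest n that reaches 0.80, as stated. An independent two-sample t-test (noncentrality d√(n/2), 2n−2 degrees of freedom) has power 0.57 at 10 per group and needs 17 per group. The stated figure therefore matches a within-person comparison. I read baseline walking in II.B.3 as the tied-belt baseline period; Figure 2 itself is not shown.

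**2. Look for that comparison in V.C.** Three factors with all interactions give 3 main effects + 3 two-way + 1 three-way = 7 Type III terms. Three readings of the outcome are possible:

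- *A between-period change* (closest to III.D.1). The hypothesis is then that the mean change differs from zero. That concerns the model's overall mean, and an ANOVA of the seven terms does not test it.
- *The split-belt period's beta.* The tied-belt data are not in the model.
- *Betas from several periods together.* No term separates the periods.

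On each reading, 0 of 7 terms test the contrast. The post-hoc rule does not help, because it follows up only significant effects among the same terms.

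**3. What the test would have if it were written down.** II.B.3 gives 1.01 for SMA only and names no population, so applying it to each group is an assumption. The value 0.5 is an illustrative smaller effect. Uncorrected paired power, same formula:

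| n | Source | d = 1.01 | d = 0.5 |
|---|---|---|---|
| 20 | all TENS-OFF visits, controls per II.A | 0.990 | 0.56 |
| 30 | all TENS-OFF visits, people with MS | >0.999 | 0.75 |
| 10 | Aim 1 set, about half of 20 controls | 0.811 | – |
| 15 | Aim 1 set, about half of 30 controls (TENS Protocol) | 0.953 | – |

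Each participant contributes one TENS-OFF visit. With balanced orders, adjusting for visit costs one degree of freedom (n−2 in place of n−1). Power with 20 and 30 participants is then unchanged to two decimals.

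**4. If Benjamini–Hochberg covers the four regions within group.** Simulation, 200,000 runs per case, correlation between regions assumed 0, 0.5 or 0.8. Power for SMA at d = 1.01:

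| n | all four regions have d = 1.01 | only SMA does |
|---|---|---|
| 10 | 0.75–0.77 | 0.56–0.57 |
| 15 | 0.94–0.95 | 0.84 |
| 20 | about 0.99 | 0.95 |
| 30 | >0.99 | >0.99 |

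**The case against.** The strongest reply is that the plan is one document and should be read as a whole. III.D.1 and the Figure 2 caption say that activation will be compared between periods. If the outcome is a between-period change, the V.C model already estimates its mean, and the emmeans package named there can test that mean against zero. What is missing, on this view, is one sentence.

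Much of this stands. The intent is on record, the data will exist, and the planned software can do the test. But stating that differences will be measured and assessed does not name a contrast, a model term, a participant set or an error-control rule. V.C, the only place that specifies tests, limits follow-up to effects already in the model. The gap is cheap to close, but it is more than a missing detail, because it concerns the hypothesis that set the sample size.

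Three stronger readings are tempting and are not supported:

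- *The trial does not plan to compare the periods.* III.D.1 and the Figure 2 caption contradict this.
- *The trial is too small for the contrast.* At the plan's own effect size, all TENS-OFF visits give ample power. The low values for 10 controls depend on using only the Aim 1 set and on II.A's 20 controls; the TENS Protocol's 30 would give about 15.
- *Correction across the four regions is required and has been omitted.* The wording in V.C leaves the family open; it neither includes nor excludes the regions.

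**Conclusion.** The point holds as a gap in the specified analysis. V.C contains no planned test of split-belt against tied-belt activation, although this is the stated cortical hypothesis and the only effect behind the sample size. It should be corrected before the fNIRS data are analysed.

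The remedy needs no more participants. If 1.01 applies to each group, SMA power stays at about 0.95 or more in both groups with all TENS-OFF visits, even if the four regions are corrected together. That margin depends on the preliminary effect size: at half a standard deviation, neither group reaches 0.80 even without correction. The participant set matters mainly for controls, and its effect cannot be settled until the two control counts are reconciled.

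**What to change.** In V.C:

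1. Define the fNIRS outcome, for each of SMA, PMC, S1 and PPC, as split-belt minus tied-belt HbO beta at each visit. Keep the planned model on this outcome for the TENS, visit and group effects.
2. Pre-specify the test of the cortical hypothesis as the estimated marginal mean of that difference under TENS OFF, against zero, in each group. Use all TENS-OFF visits, adjusted for visit. TENS-ON visits do not isolate the belt effect, because stimulation is applied in the split-belt period and not in the tied-belt period.
3. Fit this test separately by group from the start, so that it does not assume equal variances and the choice of model does not depend on a later check.
4. State whether the Benjamini–Hochberg family includes the four regions. Either answer can be defended if it is fixed in advance.
5. Reconcile the number of controls in II.A (20) with that in the TENS Protocol (30).

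The cost is SAP wording: no new data, visits or participants. If the four regions are corrected together, SMA power with 20 controls at d = 1.01 falls from 0.99 to 0.95 when only SMA responds, and hardly changes when all four do.

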- 3 Trained graduate students and the principal investigator will determine whether the subject is able to give consent. People with cognitive impairments and minors will be excluded from this study due failing to meet the inclusion/exclusion criteria.

D. Specific procedures and techniques used throughout the study

1. Laboratory tests
 - **Gait Adaptation.** This will be assessed using inertial sensors and 3-D motion capture. Both use noninvasive markers that are placed on the lower limbs of the participants. Our outcome measures assessing gait adaptation will be step length asymmetry (SLA). Step length is quantified by the anterior-posterior distance between heel markers at leading limb heel strike. Step length asymmetry will be calculated by subtracting the step length of the less affected limb from the step length of the more affected limb for each consecutive step and normalized to participant stride lengths and will be assessed continuously throughout each gait trial. We will use step length asymmetry to identify 1) the adaptation rate during the split-belt adaptation period to assess speed of adaptation between conditions and groups, and 2) adaptation savings, or the difference in adaptation rate between visit 2 and visit 1, to quantify adaptation retention between conditions and groups.

INSTITUTIONAL REVIEW BOARD NON-EXEMPT PROTOCOL TEMPLATE

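### Adaptation savings is one value per participant, so the repeated-measures model named for it cannot be run, and the natural substitute does not measure retention

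*Combined protocol and SAP*

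**What the plan says.** The Study Objectives (I.A.2) hypothesise that TENS during training increases gains in gait symmetry and "will also result in improved adaptation retention". The outcome meant to carry retention is defined under Gait Adaptation (III.D.1): "adaptation savings, or the difference in adaptation rate between visit 2 and visit 1, to quantify adaptation retention between conditions and groups".

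The design (II.A) has two sequences only, OFF then ON and ON then OFF, four weeks apart.

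The Statistical Analysis Plan (V.C) sets one model for all adaptation and fNIRS outcomes. Its fixed effects are group, visit, TENS condition and all their interactions, and participant is a random effect. It then says that "a repeated measures ANOVA will be performed for each adaptation outcome (adaptation rate and adaptation savings) and for cortical activation (HbO beta"). Follow-up is general: "Post-hoc comparisons will be conducted using estimated marginal means (EMM) to further investigate significant main effects and interactions". Multiplicity is handled by Benjamini-Hochberg (BH), "false discovery rate within each outcome and group when applicable". No section gives savings a model of its own or mentions a sequence or carryover term.

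**The concern.** A visit 2 minus visit 1 difference has already used up the visit factor, and every such difference contains one ON and one OFF visit. Nothing is left to repeat within a participant, so the analysis named for savings does not exist. The analyst would have to improvise, after seeing data, on the outcome linked to the retention hypothesis.

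The obvious improvisation carries two risks. It restates the TENS result on adaptation rate and could be reported as separate confirmation. It could also be read as evidence on retention, where a TENS effect that works would tend to make the TENS-first sequence look worse.

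**Working it through.** **The plan's own figure.** II.B.3 gives an effect size of 1.01, alpha 0.05 and power 0.8, hence at least 10 per group. A two-sided paired t test (noncentral t) gives power 0.756 at n = 9 and 0.811 at n = 10, so the figure reproduces. It concerns SMA activity from baseline to split-belt walking. The documents give no TENS effect size, so those used below are assumptions.

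**Can the model be fitted?** Inputs: 30 PwMS and 20 controls (II.A), two sequences, assumed evenly split (15/15 and 10/10). The TENS Protocol (III.D.2) has 30 controls; the two must be reconciled, but the argument is the same for either.

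- Adaptation rate: 100 rows, 8 fixed-effect columns, rank 8. The model is estimable.
- Savings: 50 rows. Visit has one level. With TENS coded as the visit 2 condition, the 8 columns have rank 4.
- Random effect: 50 participant levels for 50 observations, so it cannot be separated from the residual. lme4, which V.C names, stops with an error for this reason.
- Copying each savings value into both visit rows gives a within-person change of exactly 0.

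**What does the natural substitute estimate?** Assume additive effects and that a higher rate is better. Let p be the visit effect, d the immediate TENS benefit (the same at both visits), and k the part of it still present at visit 2.

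- TENS-first: visit 1 has d, visit 2 has p + k. Savings = p + k - d.
- TENS-second: visit 1 has 0, visit 2 has p + d. Savings = p + d.
- Difference, first minus second: (p + k - d) - (p + d) = k - 2d.
- Crossover TENS effect on rate: half of [(d - p - k) + (p + d)] = d - k/2.

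The savings difference is therefore -2 times the TENS effect on rate, with the same |t|. In one simulated complete dataset, |t| for visit, group x visit, TENS and group x TENS on rate was 1.838, 1.592, 2.592 and 2.640. The four terms of the savings model (intercept, group, sequence, group x sequence) gave the same four values. The sign depends on labelling: coded by the visit 2 condition it looks like support for TENS; coded by sequence it looks like poorer retention after TENS-first.

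**How likely is a misleading retention result?** Let dz be d divided by the SD of the within-person visit difference, and f = k/d. In PwMS (15 v 15), the standardized savings difference is (f - 2)dz, its standard error is sqrt(1/15 + 1/15) = 0.365, and the residual df in the group x sequence model are 50 - 4 = 46. At dz 0.53 the differences are -1.06, -0.80 and -0.53 for f = 0, 0.5 and 1, with noncentralities of -2.90, -2.18 and -1.45. Chance of a significant result that TENS-first retains less:

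| Assumed dz | f = 0 | f = 0.5 | f = 1 |
|---|---|---|---|
| 0.3 | 36% | 23% | 12% |
| 0.53 | 81% | 57% | 30% |
| 0.8 | 99% | 90% | 57% |

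The chance of significance in the hypothesised direction is under 0.1% at dz 0.53 and at most 0.3% at dz 0.3. With PwMS-only df (28), the middle row is 80/56/29%.

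**Visit x TENS on rate and HbO beta.** With visit and TENS coded -1/+1, their product equals sequence in all 100 rows and does not vary within a participant. Group x visit x TENS is likewise group x sequence. Under no effect (simulated, within-person correlation 0.3 to 0.85), slicing visit x TENS by visit, with BH over only those two contrasts, raises false TENS claims from 5% to 7.6-8.7%. If BH also covers the seven omnibus terms, the rate is 1.5-3.1%.

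**The case against.** - **The algebra is conditional.** k - 2d needs additivity and the same d at both visits; if TENS acts differently at visit 2, it fails. The table also takes k to be no larger than d. This stands, and the result is stated with those conditions. That the model cannot be fitted depends on none of them.
- **The match in t needs complete data.** III.F foresees participants who finish only the first day, and III.N.3 ends participation after a fall. The mixed model for rate keeps one-visit participants; savings drops them. With 5 to 8 of 50 missing visit 2, simulated t values were close but not equal (for example 3.05 v 2.87). This stands, so the claim is limited to participants with both visits.
- **A reader might infer that the whole group x visit x TENS analysis is invalid, or that visit x TENS will produce false TENS claims.** The documents do not support that. The model is estimable for adaptation rate and fitting the interaction is legitimate. V.C does not say it will be sliced by visit, and its BH wording does not fix the family. ON v OFF at visit 1 is a valid comparison of randomized arms. The term also mixes a true TENS-by-visit effect with sequence and carryover, so calling it carryover alone would be wrong too.
- **A reader might infer that lacking a lead TENS test in PwMS is an error.** I.A.2 says the effect "on gait adaptability in PwMS will be tested with active and inactive TENS during split-belt treadmill sessions", and V.C mentions primary outcome models without defining them ("Separate regression models will be conducted to assess the influence of demographic covariates on primary outcome models"). But the hypothesis sentence names no group, and I.A.2 also says that "the effect of TENS on gait adaptability will be compared between neurotypical adults and PwMS". Ranking PwMS first is a choice with costs both ways.

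**Conclusion.** The point holds for adaptation savings and should be corrected before analysis. That the named analysis cannot be run follows from the plan's own definition and needs no numerical assumption. That the substitute duplicates the TENS test on rate is exact in participants with both visits. That it misleads on retention rests on additivity and a constant d: TENS-first then looks worse unless k exceeds 2d. The size, about 81/57/30% at 0/50/100% persistence, rests on an assumed dz of 0.53 in 30 PwMS and runs from 12% to 99% over the range shown.

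The visit x TENS matter is a minor clarification, since inflation needs both visit slicing and a narrow BH family. The missing lead contrast is a matter for consideration and does not carry the point.

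**What to change.** SAP wording only; no new data.

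1. **Savings.** Remove it from the repeated-measures model. Analyse it as a between-participant comparison, group x sequence, in participants with both visits and with no participant random effect. State that in those participants its terms repeat the visit, group x visit, TENS and group x TENS tests on adaptation rate, so it is not independent confirmation. State also that the sequence difference in savings is not evidence that TENS improves or worsens retention.
2. **Minor, for adaptation rate and HbO beta.** State that visit x TENS and group x visit x TENS are between-participant contrasts in which sequence, carryover and a true TENS-by-visit effect cannot be separated. Report them with confidence intervals, and do not use their significance to open visit-specific TENS claims.

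The cost is one of scope: the trial must accept that savings cannot test the retention hypothesis in I.A.2.

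**For consideration only.** V.C could name a lead TENS contrast. Testing ON minus OFF in PwMS whatever the omnibus shows avoids a power loss from gating (control effect none/half/same) of about 12/10/5 points at dz 0.3, 14/8/1 at 0.53 and 3/1/0 at 0.8. Against that, if controls respond equally the pooled test is stronger (95% v 81% at dz 0.53).

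### The plan promises a test of TENS in people with MS, but the ON-OFF contrast in that group is written only as a follow-up to significant F tests and can go unestimated

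*Combined protocol and SAP*

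**What the plan says.** Section I.A.2 (Study Objectives) commits the trial to a PwMS-specific question: "the effect of split-belt treadmill training coupled with TENS on gait adaptability in PwMS will be tested with active and inactive TENS". The hypothesis in the same section is worded without naming a group: "the application of TENS during split-belt treadmill training will significantly increase gait symmetry improvements when compared to split-belt treadmill training alone". That section also says the TENS effect will be compared between neurotypical adults and PwMS.

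Section V.C (Statistical Analysis Plan) fits a linear mixed model with group, visit and "TENS condition (TENS ON vs. TENS OFF), along with their interactions, as fixed effects, and participant number as a random effect". Testing is by F tests: "Type III ANOVAs with Satterthwaite's method for degrees of freedom estimation will be used for all analyses". Contrasts come afterwards: "Post-hoc comparisons will be conducted using estimated marginal means (EMM) to further investigate significant main effects and interactions". On multiplicity it says "P-values will be corrected using the Benjamini–Hochberg false discovery rate within each outcome and group when applicable", and on effect sizes "Cohen's d will be calculated to quantify effect sizes". Tests are "two-tailed with an alpha threshold set at 0.05". No contrast is named as planned or primary, and confidence intervals are not mentioned.

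**The concern.** The two TENS-related F tests answer different questions from the one promised for PwMS. With Type III tests, the TENS main effect gives PwMS and controls equal weight, so if controls do not respond it targets half the PwMS effect. The group-by-TENS term asks whether the groups differ and carries the sampling error of the smaller control group. Under the coding that suits Type III tests, no single model coefficient equals the ON-OFF difference in PwMS. It has to be requested as a contrast, and the plan requests contrasts only in connection with significant terms.

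A real effect in PwMS could thus miss both F tests, and the plan would then require no estimate or interval for it. A reader could not tell an absent effect from one measured too imprecisely. When the contrast is reported only after a significant F test, its estimate is also selected, and at moderate power it is too large on average.

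**Working it through.** **The plan's own figure.** Section II.B.3 gives an effect size of 1.01, alpha 0.05, power 0.8 and at least 10 participants per group. A two-sided paired t test gives power 0.756 at n = 9 and 0.811 at n = 10, so the figure reproduces. It concerns change in activity of the supplementary motor area from baseline walking to split-belt walking, and says nothing about the size of a TENS effect.

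**Inputs.** From the documents: 30 PwMS and 20 controls (Section II.A; Section III.D.2, TENS Protocol, says 30 controls, so both were run), two-sided 0.05, two visits per person. Assumed: SD of the ON-minus-OFF difference equal to 1 in both groups, sequences balanced, no carryover or dropout, one value per person per visit, and a range of TENS effects. Four group-by-sequence cells leave 50 − 4 = 46 degrees of freedom; the critical t is 2.013.

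**Power of each test, PwMS effect 0.53, control effect 0.**
- PwMS contrast: SE = 1/√30; noncentrality 0.53 × √30 = 2.90; power 0.81.
- TENS main effect: estimate (0.53 + 0)/2 = 0.265; SE = ½√(1/30 + 1/20) = 0.144; noncentrality 1.84; power 0.44.
- Group by TENS: estimate 0.53; SE = √(1/30 + 1/20) = 0.289; noncentrality 1.84; power 0.44.

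**Effect of the gate.** By simulation, the PwMS contrast was examined only if the TENS or the group-by-TENS test had p < 0.05. *Gated* means that the gate opens and the contrast is then significant. *Skipped* is the share of trials with the gate shut among those whose PwMS contrast would itself be significant. *Ratio* is the mean estimate with the gate open, divided by the true effect.

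| Controls (n) | Effect PwMS / controls | Direct power | Gated power | Gate shut | Skipped | Ratio |
|---|---|---|---|---|---|---|
| 20 | 0.30 / 0 | 0.362 | 0.245 | 67% | 32% | 1.50 |
| 20 | 0.50 / 0 | 0.763 | 0.615 | 34% | 19% | 1.17 |
| 20 | 0.53 / 0 | 0.813 | 0.671 | 30% | 17% | 0.60/0.53 = 1.13 |
| 20 | 0.70 / 0 | 0.964 | 0.897 | 10% | 7% | 1.04 |
| 20 | 1.01 / 0 | 1.000 | 0.997 | 0.3% | 0.2% | 1.00 |
| 20 | 0.50 / 0.50 | 0.762 | 0.745 | 7% | 2% | 1.03 |
| 30 | 0.50 / 0 | 0.767 | 0.676 | 28% | 12% | 1.15 |

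With equal effects of 0.53, direct power is 0.810 and gated power 0.798, a loss of 1.2 points. With 30 controls and effects 0.53 / 0, gated power is 0.73.

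**Choice of correction family.** The 0.81 is at unadjusted 0.05, which is what a family of one contrast per outcome and group implies. If the PwMS contrast, the control contrast and their difference were instead pooled in one Benjamini-Hochberg family, power for the PwMS contrast with 20 controls would be 0.68 at 0.53 / 0 (gated 0.67), 0.42 at 0.40 / 0 (gated 0.42) and 0.72 at 0.53 / 0.53 (gated 0.80). Pooling would give back almost all the gain, or more than all of it.

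**Scope.** Adaptation savings is defined in Section III.D.1 as visit 2 minus visit 1, one value per person, so it has no within-person ON-OFF difference and these figures do not apply to it.

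**The case against.** Omnibus test followed by post-hoc comparison is a conventional procedure, and the sponsor can fairly say that its hypothesis names no group. The always-run TENS main effect tests that hypothesis, and the always-run group-by-TENS term tests the promised comparison between groups. This stands: a reader might infer that the TENS effect as such can escape testing, and the documents do not support that. Only the PwMS-specific contrast is at risk.

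A reader might also infer that every reported estimate will be inflated. That is not so. The bias is an average over trials, a single estimate may be too low, and the table shows it fading with large effects or with equal effects in both groups. At 0.53 / 0, requiring the contrast to be significant as well as the gate open gives a mean of 0.62, but that significance filter alone gives 0.59 without any gate.

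Nor does the plan contain the word *only*, make Cohen's d conditional on significance, or say that non-significant contrasts go unreported. Gating is the natural reading of the sentence, not an explicit prohibition. A harsher gate, in which only the interaction licenses within-group contrasts, would lower power at 0.53 / 0 to 0.42, but the plan does not state it. Finally, the absence of any effect in controls is an assumption made here.

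What the objection does not meet is the gap between the two sections: one promises a result for PwMS, and the other does not require it.

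**Conclusion.** The concern holds in limited form. The PwMS-specific ON-OFF contrast is promised but not prespecified, and as written it can go unestimated, even in trials where it would have been significant. With 30 PwMS, 20 controls, 0.53 SD in PwMS and none in controls, the gate costs 14 points of power (0.81 to 0.67), stays shut in 30% of trials, and raises the mean estimate to about 0.60 when open. The cost shrinks to about one point with equal effects, and gated power is 0.73 with 30 controls. These figures rest on assumed effect sizes, because the documents give none for TENS. They apply to adaptation rate and HbO beta. The omission does not invalidate the planned analysis. It is a gap in what must be reported, worth closing because closing it is nearly free.

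**What to change.** In Section V.C, add wording to this effect: *For adaptation rate and HbO beta, TENS ON minus OFF in PwMS, the same contrast in controls, and the difference between the two will be estimated from the model with 95% confidence intervals, whatever the results of the F tests. The PwMS contrast is the planned test. Benjamini-Hochberg correction is applied within outcome and group and is not pooled over these three contrasts. Other EMM comparisons may follow significant terms.*

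The cost is SAP wording; no participants, visits or measurements are added. The downside is that one planned test per outcome no longer depends on the omnibus result, so the members of each correction family must be stated in advance. In particular, the plan should say whether HbO beta in several cortical regions counts as one outcome or several, because the 0.81 assumes a single PwMS contrast in the family.
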